5.1 Blinding, Randomization, Stratification, and Treatment Assignment

Treatment kits will be blinded and numbered. The two treatment arms are not distinguishable at the site. Therefore the study team, the pharmacy, and the monitors will be blinded.

The randomization scheme will be prepared by the sponsor. Those unblinded are limited to the statistician not involved with the study who generated the randomization code, and the pharmaceutical group that packaged the study drug. The Data and Safety Monitoring Board (DSMB) will have access to the unblinding code in a sealed envelope.

The study will remain blinded until after the last subject enrolled has completed the last follow-up visit and all data queries have been resolved. The study will then be unblinded for analysis.

Randomization will be built into the treatment kit order at each site (i.e., kit #101 may be NTZ or PCB depending on the randomization scheme).

Randomization will be stratified by sites and by adult and pediatric (<12 years). Randomization will occur in blocks of 4. Each site will receive study drug in multiples of 4, thus ensuring randomization is balanced by site.

Subjects who meet all criteria for enrollment will be assigned the next study kit at a site. Kits will be assigned in a consecutive manner starting with the first kit number in the block at each site.

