8.7.7.1 Interim Analysis

The study will undertake a formal interim efficacy examination. An unblinded statistician that is not associated with a site, not part of the protocol team and not part of the operational support for this study will perform this analysis.

After half of the total sample size has completed 28 days of follow-up, primary analysis using the Fay-Shaw statistic (13) will be conducted. The study will be stopped for benefit if the one-sided p-value for benefit is less than .001. The study will be stopped for futility if the one-sided p-value for harm is less than .025.

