9.1 General Considerations

This is a double-blind, randomized, placebo, controlled trial in patients with hospitalized influenza-like-illness to evaluate the efficacy of NTZ compared to placebo on the time to hospital discharge. The primary analysis will use the Shaw-Fay formulation of the 2 sample Mann-Whitney-Wilcoxon rank-sum statistic. The primary endpoint will be time to hospital discharge, censored at 28 days. Patients who withdraw consent will be counted as being censored at the time of withdrawal. Patients who die by Day 28 will receive the worst ranks, (i.e., worse than any patients who remain hospitalized). Furthermore, patients who die earlier will receive worse ranks than those who die later. Patients who withdraw consent prior to day 28 are thus censored for death and discharge at the time of withdrawal. Such censoring is addressed by the method of Shaw and Fay (2013). A permutation method will be used to determine statistical significance. The primary analysis will follow the intent-to-treat principle where all randomized patients will be used in the analysis. The primary analysis will use a two-sided alpha level of .05.

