9.2 Sample Size and Power Calculations

Sample size calculations are based on the primary endpoint only (i.e. Duration of hospitalization). Secondary endpoints may or may not be adequately powered with the chosen sample size.

When there is no censoring or deaths, power for the two-sample Mann-Whitney-Wilcoxon rank-sum test can be approximated assuming that days of hospitalization follows a log normal distribution. The parameters used in the calculation were from the observed distribution of days to hospital discharge for hospitalized subjects who enrolled in the ILI002 observational study. We obtained data on patients who survived with hospitalization less than 28 days. The data were truncated at 28 days to avoid the influence of aberrant values on the estimates. This eliminated about 4% of the data. The mean and variance of the days in the hospital were 7.7 and 33.2. We assumed that the effect of treatment would be to reduce the number of days in the hospital by Delta but that there would be no effect of treatment on the variance of the number of days in the hospital. Thus for the treatment group the mean and variance are given by 7.7-Delta and 33.2, where Delta is varied. We next assume that the distribution of days to hospital discharge followed a log-normal distribution in each group, which is equivalent to assuming that the log(Days) follows a normal distribution, where Days is the number of days until hospital discharge. A log-normal distribution is specified by its moments $E\{\log(Days)\} = m$ and $\text{var}(\log(Days))=v$. These moments are related to the mean, $E(D)$, and variance, $V(D)$, of the number of days (D) in the hospital by the formulas.

$$m = \log\{E(D)\} - v/2$$

$$v = \log\{1 + V(D)/[E(D) \times E(D)]\}.$$

For simplicity, we determine the sample size for different assumptions of treatment effects of nitazoxanide, using a two sample t-test with unequal variances using Satterthwaite's method (Table 8). This method requires the mean and variance of log (Days) for the 2 groups, which are obtained by solving the above equations separately for the placebo and treatment groups. Calculations were performed using Nquery 7.0.

Table 9: The total sample size required to achieve different powers under different assumptions about the benefit of nitazoxanide (Delta) using a two-sided .05 level test

Moments for the log days in hospital						
	Placebo Group		Treatment Group			
Delta ^a	m ₀₀	Sqrt(v ₀)	m ₀	Sqrt(v ₀)	Power	N ^b

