## 11. Primary Endpoint (ITT, ITT age subgroups, ITT pediatric formulation subgroups, ITT virology subgroups)

Table to show the completeness of the primary endpoint should include number (%) with [14.2.2]:

- Complete data (Day of hospitalization and discharge or death)
- Incomplete data (missing day of hospitalization or discharge/death)

The following table and figure provide descriptive statistics of the primary endpoint. The table and figures should impute values of 28 days for patients who died and should censor patients with missing discharge date at the time of last follow up.

- Figure: Kaplan-Meier plot of time to hospital discharge/death (only ITT and ITT age subgroups)
- Table: with the following estimates from the Kaplan-Meier curves- 25th, 50th and 75th percentile along with min and max values in hours [14.2.3.1.x]

- The between group difference in median time to discharge will be used to estimate the treatment effect and will be reported along with a 95% two-sided confidence interval.
- Additionally, data from median, min, max converted to “days, hours”
- The p-value for the 2 group comparison of the primary endpoint analysis will be performed using the Shaw-Fay method as described in appendix 1.
- Sensitivity analyzes to exam effect of missing death or discharge data. (only ITT and ITT age subgroups)
  - Figure with Kaplan-Meier curves and Shaw-Fay p-values on the ITT only where missing death or discharge dates are imputed in the placebo group as censored at the time of last follow up and in the experimental group are imputed as events at day 28.
  - Figure with Kaplan-Meier curves and Shaw-Fay p-values on the ITT only where missing death or discharge dates are imputed in both groups as events at day 28.
  - For any imbalance seen in baseline characteristics ( $p < .05$ ) perform a cox proportional hazards model with deaths receiving event times of 28 days. Missing discharge dates will be censored at last follow up time.

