    - P-value obtained using Shaw-Fay method (here only treat deaths as worst rank and missing as censored)
  - Table duration of oxygenation: defined as time of oxygen first administered, to time off oxygen (in hours) noting min, 25%tile, 50%tile, 75%tile, max [14.2.5.3.x]
    - Table is restricted to those requiring oxygen at any point during the study.
    - P-value obtained using Shaw-Fay method (here only treat deaths as worst rank and missing as censored)
  - Figure using Kaplan-Meier plot
    - Figure includes all subjects – where subjects not requiring oxygen have 0 hours.
    - Figure is repeated, but restricted to those requiring oxygen at any point during the study.
- Admission to ICU
  - Table N (%) of requiring ICU (Y/N) at any point during the study, and at each time point [14.2.6.1.x]
    - P-value obtained using test of proportions
  - Figure of proportions at each time point
  - Table duration of ICU: defined as time subject admitted to ICU, to time discharged from ICU (in hours) noting min, 25%tile, 50%tile, 75%tile, max [14.2.6.2.x]
    - Table includes all subjects – where subjects not requiring ICU have 0 hours.
    - P-value obtained using Shaw-Fay method (here only treat deaths as worst rank and missing as censored)
  - Table duration of ICU: defined as time subject admitted to ICU, to time discharged from ICU (in hours) noting min, 25%tile, 50%tile, 75%tile, max [14.2.6.3.x]
    - Table is restricted to those requiring ICU at any point during the study.
    - P-value obtained using Shaw-Fay method (here only treat deaths as worst rank and missing as censored)
  - Figure using Kaplan-Meier plot
    - Figure includes all subjects – where subjects not requiring ICU have 0 hours.
    - Figure is repeated, but restricted to those requiring ICU at any point during the study
- Intubation/mechanical ventilation
  - Table N (%) of requiring mechanical ventilation (Y/N) at any point during the study, and at each time point [14.2.7.1]

- P-value obtained using test of proportions
- Figure of proportions at each time point
- Table duration of mechanical ventilation: defined as time subject placed on mechanical ventilation, to time extubated (removed from mechanical ventilation) noting min, 25%tile, 50%tile, 75%tile, max [14.2.7.2.x]
  - Table includes all subjects – where subjects not requiring mechanical ventilation have 0 hours.
  - P-value obtained using Shaw-Fay method (here only treat deaths as worst rank and missing as censored)

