- Evaluate the virologic efficacy of NTZ + SOC vs. PCB + SOC with regards to:  
Restricted to those with virus detectable on Day 0
  - Table N (%) of subjects that had any virus detectable on Day 0, and no longer had any virus detectable on Day 3 [14.2.11]
    - If more than one virus was present on Day 0, both viruses must be cleared to be considered as no detectable virus. If Day 3 has a virus that was not detected on Day 0 (day 0 had virus A and Day 3 virus B), this is not considered as having no detectable virus.
    - P-value obtained using test of proportions
  - Table N (%) of subjects that had virus detectable on Day 0, and had a different virus detectable on Day 3.

## Appendix 1

The primary endpoint is time to hospital discharge or death within 28 days. The primary analysis will follow the intent to treat principal where all patients randomized will be used in the analysis and analyzed according to treatment assignment. Observations will be censored at 28 days if discharge or death does not occur before 28 days.

The Shaw-Fay methodology uses ranks to form the test statistic. The following ranking system will be followed if no loss to follow up occurs. Patients who die will be given worse ranks than those who are alive. Among those who die, early deaths receive worse ranks than those who are alive and among those alive the order of ranking from worst to best is no discharge, late, than early discharge. Table 1 gives an example of rankings for an invented data set.

Table 1. Example of rankings for invented data set. C indicates censored at day 28 or censored due to death. Larger ranks are worse than smaller ranks.

Person	Day of discharge	Day of Death	Rank
1	C	5	8
2	C	10	7
3	3	15	6
4	C	C	5
5	15	C	4
6	5	C	3

7	2	C	1.5
8	2	C	1.5

The test statistics is the sum of the ranks for patients in the Nitazoxanide group. Treatment labels will be permuted to calculate the probability of obtaining a test statistic as extreme as the observed sum of the ranks of the experimental group.

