If patients are lost to follow up (i.e. withdraw consent) prior to day 28 the Shaw-Fay formulation of the 2 sample Mann-Whitney Wilcoxon rank-sum statistic will be formed. Ranks for observed data will be as described above and ranks for those with missing data will be as described in Shaw-Fay. R code will be provided that calculates the ranks for those patients who are lost to follow up. The rank based permutation test as described above will be used to calculate the test statistics.

Reference: Shaw, Pamela A., and Michael P. Fay. "A rank test for bivariate time-to-event outcomes when one event is a surrogate." *Statistics in Medicine* 2016; 35(19): 3413-3423.

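### The primary permutation test is not tied to the site-by-age randomisation strata, so it is conservative if those strata predict length of stay

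*SAP*

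**What the plan says.** Protocol section 5.1 sets the allocation scheme: "Randomization will be stratified by sites and by adult and pediatric (<12 years). Randomization will occur in blocks of 4". Protocol section 3.4 allows up to 8 sites, so there can be up to 16 strata.

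For the primary test, protocol section 9.1 says only "A permutation method will be used to determine statistical significance". SAP Appendix 1 takes the rank sum over the whole nitazoxanide arm as the statistic and continues: "Treatment labels will be permuted to calculate the probability of obtaining a test statistic as extreme as the observed sum of the ranks". When patients are lost to follow-up, it refers back to the same scheme: "The rank based permutation test as described above will be used to calculate the test statistics". The R code promised there is for the ranks of patients lost to follow-up. It is not described as defining the permutation.

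The same test drives the interim look in protocol section 8.7.7.1: "After half of the total sample size has completed 28 days of follow-up, primary analysis using the Fay-Shaw statistic (13) will be conducted". The benefit bound is a one-sided p below .001, and the bound for harm is a one-sided p below .025.

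The only covariate adjustment is in SAP section 11: a Cox model, listed as a sensitivity analysis, for baseline characteristics that are imbalanced at p < .05.

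**The concern.** A permutation test takes its null distribution from the allocations that could have occurred. Stratified blocks rule out most allocations in which one arm is heavy in a particular site or age group. A free shuffle puts those allocations back. If stay differs by site or age, they add spread that the actual design does not have, and p-values are then too large on average.

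Differences by stratum are plausible. The treating physician decides discharge (protocol section 3.4), and no standard-of-care regimen is mandated (section 5.6). In protocol Table 2 the pathogen mix differs by age: RSV in 44 of 253 children against 35 of 1,123 older patients.

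At stake are the power of the primary test and the calibration of the interim p-values. A secondary matter is that an unnamed scheme leaves a choice that could be made after unblinding.

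**Working it through.** **The plan's own figure.** Protocol section 9.2 sizes the trial "using a two sample t-test with unequal variances" on log days. The printed moments for the 1.25-day row are 1.83 (SD .66) on placebo and 1.58 (SD .76) on treatment. With 129 per arm, SE = √[(.66² + .76²)/129] = .0886. The noncentrality is .25/.0886 = 2.82, and power is 80.2%. The stated 258 is reproduced. 258/.9 = 286.7, so 287 patients cover 10% dropout, and the plan recruits 290. This calculation uses no strata.

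**The two null variances.** Let S be the nitazoxanide rank sum, N the total, k₁ the number on nitazoxanide and s² the variance of all ranks. Let n, k and s²ⱼ be the size, number on nitazoxanide and rank variance of stratum j.
- Free shuffle: Var(S) = s²·k₁(N − k₁)/N.
- Within strata: Var(S) = Σⱼ s²ⱼ·k(n − k)/n.

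The second leaves out the between-stratum variation. If the true variance is a fraction v of the free-shuffle variance, the nominal 5% test has size 2[1 − Φ(1.96/√v)].

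**Simulation 1: final analysis, N = 258, 10,000 trials per setting and hypothesis.**
- 8 sites with assumed shares 24/18/15/12/10/9/7/5%.
- 18.4% children (253/1,376, protocol Table 2).
- Blocks of 4 within 16 strata, and log stay normal with the moments above.
- R² is the assumed share of log-stay variance explained by strata, split equally between site and age.
- No deaths, censoring or time trend.

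| R² | Size, free | Size, within | Power, free | Power, within |
|---|---|---|---|---|
| 0% | 5.2% | 5.2% | 78.2% | 77.8% |
| 5% | 4.5% | 5.0% | 79.1% | 80.2% |
| 10% | 3.8% | 4.9% | 79.9% | 82.5% |
| 20% | 3.0% | 4.8% | 81.3% | 86.2% |

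**Interim analysis, N = 290/2 = 145, same set-up.** The benefit columns assume the 1.25-day effect; the harm columns assume no effect.

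| R² | Benefit bound, free | Benefit bound, within | Harm bound, free | Harm bound, within |
|---|---|---|---|---|
| 0% | 14.0% | 13.2% | 2.5% | 2.5% |
| 5% | 13.5% | 14.3% | 2.3% | 2.6% |
| 10% | 13.1% | 15.6% | 1.9% | 2.3% |
| 20% | 12.3% | 19.0% | 1.5% | 2.2% |

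**Simulation 2: different assumptions, N = 290.** This run assumed 25% children and 4% deaths given the worst ranks, with stay censored at day 28, no dropout and moments taken unrounded from 7.7 and 33.2. There were 12,000 null and 6,000 alternative trials per setting. With 8 sites and R² of 0/5/10/20%:
- The variance ratio v was 1.00/.96/.92/.85.
- Free-shuffle size was 5.3/4.4/4.0/3.5%. As a check, v = .848 (the unrounded value at 20%) gives 1.96/√.848 = 2.13 and hence 3.3%.
- Power, free against within strata, was 74.5/74.2, 75.0/76.0, 76.4/78.8 and 77.6/82.6%.

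Power here should be compared only between schemes, because deaths and the rank test move it away from the stated 80%. Six sites gave the same pattern.

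**Cost of sparse strata.** Information lost is 1 − Σⱼ[k(n − k)/n] ÷ [k₁(N − k₁)/N]. This is about 0.9% at N = 258 and 2.5% at N = 145. For assumed subset sizes of 60, 30 and 20 patients it is about 18%, 32% and 43%.

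**The case against.** The strongest reply is that this is a missed efficiency and not an error. The free shuffle does not inflate type I error. Its power rises from 78.2% to 81.3% across the range, so the trial gets roughly what protocol section 9.2 promises. A mildly conservative test that matches an unstratified sample-size calculation is defensible. That stands, and it limits the weight of the point.

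The gain also rests on an R² the documents do not give. At 5% it is about 1 point (80.2 − 79.1). Gains near 5 points need about 20%, which nothing in the documents supports or excludes. That stands too. However, the trade is lopsided: 0.4 points of final power lost if strata are uninformative, against 4.9 gained at 20%.

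Three further limits are fair. Within-stratum permutation is closer to the design but does not reproduce the blocks of 4. Table 2 counts children from 2 years, whereas the trial enrols from 12 months, so 18.4% may be too low; the second run, at 25%, shows the same pattern. Simulation 1 has no deaths; simulation 2 has them and agrees in direction.

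It can also be said that Appendix 1 already implies a free shuffle, leaving little room for a late choice. That makes the unblinding worry secondary but does not remove the mismatch with the design.

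**Conclusion.** The concern holds. Neither document ties the primary permutation test to the strata used for randomisation, and nothing else in the plan makes up for it: the Cox model is a triggered sensitivity analysis and does not change the primary p-value. The free shuffle is an inference from silence, though the natural one.

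If site and age explain 5 to 20% of the variance of log stay, the nominal 5% test runs at about 4.5% down to 3%, and about 1 to 5 points of power are forgone at the final analysis. At 20%, the chance of crossing the interim benefit bound is 12.3% where 19.0% was available. If strata explain nothing, there is no material difference. The direction follows from the design; the size depends on an assumed R². This should be changed, but it does not threaten the validity of the trial.

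**What to change.** Add to SAP Appendix 1, before unblinding: *Treatment labels will be permuted only within the strata used for randomisation (site by age under 12 or 12 and over, as randomised), holding the number on nitazoxanide in each stratum fixed.* Apply this to the primary ITT analysis and the interim analysis.

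Keep the Shaw-Fay scores and the rank sum. With stratum counts fixed, a stratum-centred statistic equals S − Σⱼ k·r̄ⱼ, where r̄ⱼ is the mean rank in stratum j. The subtracted term is constant under the permutation, so the statistic needs no change.

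Do not extend the rule automatically to small sets. SAP section 11 repeats the primary analysis in the "ITT age subgroups, ITT pediatric formulation subgroups, ITT virology subgroups", and section 12 has tests in restricted groups, for example "Table is restricted to those requiring oxygen at any point during the study". State the scheme for each of these separately. The SAP's age subgroups cut at 18 and 13 years, so the text should make clear that the permutation strata use the randomisation cut. The SAP's 13-year formulation cut and the 12-year cut in protocol section 5.2 also need to be reconciled.

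The cost is one sentence and a small change to the R code. If strata prove uninformative, power falls by about 0.4 points at the final analysis and 0.8 points for the interim benefit bound. If the sponsor prefers a free shuffle, the SAP should say so and acknowledge that it may be conservative.
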